## 2. List of abbreviations

ACCCOS	African COVID-19 Critical Care Outcomes Study
ACIOS	African Critical Illness Outcomes Study
APORG	(African Perioperative Research Group)
APPRISE	African Partnership on Perioperative and Critical Care Research
ASOS	African Surgical Outcomes Study
ASOS-2	African Surgical OutcomeS-2 (ASOS-2) trial
CRISPOS	Critical Illness and Sepsis Prevalence and Outcomes Study
EECC	Essential Emergency and Critical Care
EuSOS	European Surgical Outcomes Study
HDU	High Dependency Unit
ICU	Intensive Care Unit
ISOS	International Surgical Outcomes Study
NIHR	National Institute for Health and Care Research
SAP	Statistical Analysis Plan

### 3. Summary

Short title	ACIOS
Methodology	A prospective, international, multi-centre, observational study.
Research sites	Acute hospitals in African countries.
Objective	To determine the hospital point-prevalence and mortality rates of adult patients with critical illness in hospitals in Africa.
Number of patients	Not specified. All eligible patients in participating hospitals.
Inclusion criteria	All in-hospital patients aged 18 years or older in all departments and wards in participating hospitals in Africa.
Exclusion criteria	None
Patient follow-up	Until hospital discharge or death, censored at 7 days after inclusion.
Primary outcomes	1. The presence of critical illness 2. 7-day in-hospital mortality
Statistical analysis	Descriptive statistics, univariate and multivariable logistic regression models. A statistical analysis plan will be written before analysis.
Data collection duration	One day in each hospital in September-November 2023 plus 7 days follow-up in each hospital
Proposed start date	1 st September 2023
Proposed end date	7 th December 2023

#### 4. Introduction

Critically ill patients – those in *a state of ill health with vital organ dysfunction, a high risk of imminent death if care is not provided, and the potential for reversibility*. – have particular needs, and managing these needs is a core function of hospitals. Triage at admission and on the wards is needed to identify these patients with critical illness. Critically ill patients need regular contact with health workers and close observation and frequent modifications to care, either in general wards, or in specialised locations such as Intensive Care Units (ICUs) and High Dependency Units (HDUs). Rapid Response Teams of acute care specialists may be implemented in hospitals to provide care when called by ward staff.

There are reports of gaps in the readiness and provision of critical care in hospitals in Africa. Essential Emergency and Critical Care (EECC) has been developed and defined as the first-line care that should be provided to all critically ill patients. Focusing on the first-line care in EECC is a strategy to address the gap in critical care. In our previous work an unmet need of EECC of 50-90% was found in hospitals in Malawi, and there have been many calls to increase the coverage of EECC to address this gap.

While it is accepted that critical illness and the underlying causes of critical illness are common, the number of patients with critical illness has not been accurately quantified. In one region of Sweden we found 10% of hospital inpatients to be critically ill, and in a Tanzanian university hospital's emergency unit, 10% of patients were critically ill at arrival. Global estimates have been attempted by using the admission rates to ICUs but this method reflects national and local uses of ICUs which vary greatly even between high-income countries. The indirect annual global estimate of 30-45 million adults made by extrapolating the incidence of common diseases leading to critical illness in North America is likely to be an underestimate as the burden of disease is greater in settings of lower resources. Moreover, the mortality of critically ill patients has not been accurately quantified, with reports of 18-82% in-hospital mortality rates.

A patient's vital signs (heart rate, respiratory rate, blood pressure, conscious level, body temperature, oxygen saturation) are commonly used measurements in hospital care. Deranged vital signs have been shown to correlate with negative outcomes such as admission to the ICU, unexpected cardiac arrest, and mortality, and are pragmatic and useful as criteria for the identification of critical illness.

We will conduct a prospective, international, multi-centre, observational study of all adult in-patients in hospitals across Africa, based on the methods we developed in the International Surgical Outcomes Study (ISOS), European Surgical Outcomes Study (EuSOS), African Surgical Outcomes Study (ASOS), and African COVID-19 Critical Care Outcomes Study (ACCCOS) studies. Using vital-signs based criteria, we will determine the hospital point-prevalence of critical illness. We will collect data on the care provided to patients, so to determine the coverage of essential emergency and critical care. We will follow the adult in-hospital patients for 7 days or until hospital discharge (whichever is sooner), allowing an estimate of the mortality rate and patients at increased risk who are critically ill in this population. The knowledge generated in the ACIOS study will assist in improving organisation of acute hospital services with the goal of averting substantial numbers of preventable deaths in African hospitals.

## 5. Aim, Objectives, Research questions and Outcomes

### 5.1 Aim

To investigate critical illness, its care and associated outcomes among all adult inpatients in hospitals across Africa.

### 5.2 Objectives

1. To establish the proportion of adult (18 years or older) inpatients in African hospitals that are critically ill.
2. To establish the mortality rate of the critically ill patients and those who are not critically ill.
3. To estimate the proportion of critically ill patients who receive essential emergency and critical care.
4. To investigate the association between the provision of essential emergency and critical care to critically ill patients and mortality.
5. To determine the availability of resources for essential emergency and critical in African hospitals.

### 5.3 Research questions

Among adult (18 years or older) inpatients in African hospitals:

1. What proportion of patients are critically ill?
2. What are the mortality rates for patients who are, and who are not critically ill?
3. What proportion of critically ill patients receive essential emergency and critical care?
4. What is the relationship between essential emergency and critical care provision, and mortality?

In African hospitals:

5. What is the availability of resources for the provision of essential emergency and critical care?

#### 5.4 Co-primary outcomes

- Presence of critical illness
- In-hospital mortality (censored at 7-days)

#### 5.5 Secondary outcomes

- Provision of essential emergency and critical care
- Length of hospital stay

#### 5.6 Hospital level outcome

- Availability of resources for essential emergency and critical care

### 6. Methods

#### 6.1 Study design

African, multi-centre prospective observational cohort study of in-hospital adult patients.

#### 6.2 Study setting

Hospitals across Africa.

#### 6.3 Hospital participation criteria

Any acute hospital in Africa providing adult inpatient care (see Definitions section 8).

#### 6.4 Study population (patient Inclusion criteria)

All adult patients aged 18 years or over who have been admitted for inpatient care in any department or ward in participating hospitals.

#### 6.5 Exclusion criteria

None.

## 7. Study Procedures

### 7.1 Hospital Recruitment

Hospitals will be recruited through the African Perioperative Research Group (APORG) network, the Essential Emergency and Critical Care (EECC) network and other networks in Africa.

### 7.2 Study data

Data will be collected on all eligible patients on the study day and then during in-hospital follow-up.

### 7.3 Data collection

A pragmatic and realistic dataset is fundamental to the success of the study. Data will be collected on paper on one-day in each hospital plus follow-up censored at 7 days. Data will be collected:

- At hospital level for the availability of resources for EECC.
- At the patient's bedside for patient demographic and medical information, physiological signs, and ongoing provision of EECC and
- From hospital records for patient outcomes.

#### 7.3.1 Schedule of assessment

Event/ Visit	Study day	Until discharge or death, censored at 7 days
Hospital level data	X	
Inclusion/ exclusion criteria	X	
Demographic information	X	
Medical information	X	
Physiological signs	X	
EECC provision	X	
Outcomes		X

#### 7.3.2 Hospital level data collection

Data will be collected once for each hospital to assess the availability of resources for the provision of EECC. A checklist of resources will be used and data entered together with a key informant in the hospital. The key informant may be the medical-officer-in-charge or other clinician or administrator

who has an in-depth knowledge of the resources available in the hospital for managing critically ill patients, as identified by the study team's local coordinator. In addition, data will be collected on:

- Population served (catchment area)
- Primary, secondary or tertiary hospital
- Number of hospital beds
- Number and level of critical care beds
- Details about the reimbursement status of the hospital
- Resources in the hospital such as staff and equipment

#### **7.3.3 Patient level data collection**

On the specified day of data collection, every patient fulfilling the inclusion criteria in every department and ward in the hospital will be included in the study. Patients who are absent from their beds when the study team arrive, (for example, are in an operating theatre, or undergoing a medical investigation), will be re-visited later the same day and included when they are back in their bed, or when they are in a bed where inclusion is possible such as in a surgical recovery room. Data on patient demographics, medical information and current care provided will be collected from the patient and from the clinical team. The patient's vital sign measurements, (respiratory rate, oxygen saturation, blood pressure, heart rate, conscious level), will be checked by the study team using the hospital's equipment. If it is inappropriate for a patient's vital signs to be checked – for example if the clinical team has made the decision to refrain from vital sign observations as the patient is in the final stage of dying, (may be termed 'on an end-of-life pathway', "moribund", 'gasping' or 'late palliative phase' by the clinical team), or if the patient refuses permission to measure their vital signs – then the patient will be included in the study but vital signs will not be measured. It will be acceptable for the study team to record the last vital signs recorded in the patient's file for these patients. For women in active labour, the vital signs will be measured between contractions. Detailed data collection procedures will be described in the study's Standard Operating Procedures. Data will be collected by clinician investigators, and/ or clinician researchers working at the site.

#### **7.3.4 Outcomes**

The patient outcomes will be reported as alive and discharged, died, or alive and still in hospital censored at 7-days.

#### 7.4 End of Study Definition

The end of the study is defined as the end of the 7-day follow-up for the last included patient. Data analysis shall follow this.

### 8. Definitions

*Critical illness (co-primary outcome):* a state of ill health with vital organ dysfunction, a high risk of imminent death if care is not provided and the potential for reversibility. Patients will be classified as critically ill if they have one or more severely deranged vital signs as in Figure 1. The cut-offs are those used in the Critical Illness and Sepsis Prevalence and Outcomes Study (CRISPOS) study and based on previous research in Tanzania and Sweden :

Criterion	Vital signs	Definition critically ill
Conscious level	Conscious level (AVPU Scale)	P or U
Respiratory	Respiratory rate per minute	<8 or >30
	Oxygen saturation (%)	<90
Circulatory	Heart rate per minute	<40 or >130
	Systolic blood pressure (mmHg)	<90

Figure 1: Criteria for the definition of critical illness

*Hospital population:* all adult patients aged 18 years or over who have been admitted for inpatient care in any department or ward in participating hospitals on the day of data collection.

*Essential Emergency and Critical Care (EECC):* the care that all critically ill patients should receive, in all hospitals in the world including clinical processes such as oxygen therapy, intravenous fluids and patient positioning to protect the airway, as described in the 2021 global consensus.

*Availability of resources for EECC:* The 66 resources necessary for the provision of EECC including items such as pulse oximeters, oxygen masks and intravenous fluids.

*Coverage of EECC:* The proportion of critically ill patients receiving EECC.

Patients will be deemed to be receiving EECC if they are:

- critically ill due to the conscious level criterion (Figure 1) **and**:
  - are lying in the lateral position **or**

- have an oro-pharyngeal or naso-pharyngeal airway inserted in their pharynx **or**
- have an ongoing chin-life or jaw-thrust **or**
- have other airway protection
- critically ill due to a respiratory criterion (Figure 1) **and**:
  - are receiving oxygen
- critically ill due to a circulatory criterion (Figure 1) **and**:
  - are receiving intravenous fluids **or**
  - are receiving a vasopressor or inotrope

*Acute Hospital:* A hospital admitting acutely unwell patients – i.e. patients who have a recent onset or exacerbation of a somatic condition and require timely care. Acute hospitals can be owned and run by the government or by a private or other organisation. Hospitals that only admit chronically unwell patients, or only patients for rehabilitation, or only patients for elective surgery are not regarded as acute hospitals and are not eligible for participation in ACIOS. Hospitals, units and wards exclusively for patients with psychiatric conditions are not regarded as acute hospitals.

*In-hospital mortality (co-primary outcome):* Death in-hospital. Patients discharged alive are not followed-up at home.

*1-day and 7-day outcomes:* The defined time for the outcomes is from the point of inclusion of the patient into the study to hospital discharge or death, censored at 7-days.

## 9. Data Handling and Management

The papers containing identifiable patient data for the follow-up of clinical outcomes will be stored within a locked office in each hospital or institution. Data will then be pseudo-anonymised by generation of a unique numeric code and transcribed by local investigators onto an internet based electronic case-record file (e-CRF).

Each patient will only be identified on the e-CRF by their numeric code; thus the central co-ordinating study team cannot trace data back to an individual patient. A participant list will be used in each hospital/site to match identifier codes in the database to individual patients in order to record clinical outcomes and supply any missing data points. This participant list will be stored on a password-protected computer. Access to the data entry system will be based on the principle of least privilege and

will be protected by username and password delivered during the registration process for individual local investigators.

All electronic data transfer between participating hospitals and the co-ordinating institution will be encrypted using a secure protocol (HTTPS/SSL 3.0 or better). Data will be anonymised during the transcription process using the Research Electronic Data Capture (REDCap) tools hosted by Safe Surgery South Africa (SSSA) who will act as the data custodian. REDCap is a secure, web-based application designed to support databases and data capturing for research studies. Soft limits will be set for data entry, prompting investigators when data were entered outside these limits. In countries with poor internet access, paper case record forms may be forwarded to SSSA, for entry by SSSA. Pseudo-anonymised (coded) data may also be sent by encrypted e-mail to the coordinating institution if necessary. Each institution will maintain a secure trial file including a protocol, local investigator delegation log, ethics approval documentation, the participant list, etc. Copies of the relevant protocols, approvals and investigator lists will also be kept securely in an internal drive by SSSA. A final summary of included patients with aggregated data of patients, and outcomes will be produced for each hospital together with final data submission to double check for completeness and accuracy.

Individual patient data provided by participating hospitals remain the property of the respective institution, once the ACIOS report has been published. Once each local co-ordinator has confirmed the data provided from their hospital are both complete and accurate, they will be provided with a spreadsheet of the raw (un-cleaned) data for their hospital. In the ACIOS report, only summary data will be presented publicly, and all national, institutional and patient level data will be strictly anonymised.

## 10. Statistical Analysis

### 10.1 Sample size calculation

Our plan is to recruit as many hospitals as possible in as many African countries as possible. All eligible patients will be included in each hospital. We do not have a specific sample size.

### 10.2 Statistical analysis

An ACIOS statistical analysis plan (SAP) will be written prior to inspection of the final dataset. Data will be presented at a continental African level. All institutional and national level data will be anonymised prior to publication. Categorical variables will be described as proportions and will be compared using

chi-square tests. Continuous variables will be described as mean and standard deviation if normally distributed, or median and inter-quartile range if not normally distributed. Comparisons of continuous variables between groups will be performed using t-tests, one-way ANOVA or equivalent non-parametric tests as appropriate. Univariate and hierarchical, multivariable, multi-level logistic regression models will be constructed to determine the relationship between the presence of critical illness and mortality and the relationship between essential emergency and critical care provision and mortality.

Results of logistic regression will be reported with 95% confidence intervals. The models will be assessed with predefined sensitivity analyses to explore possible interacting factors and examine any effect on the results. A single final analysis is planned at the end of the study.

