**Follow-up**

Total days in hospital from admission to discharge  /

Status at 7th day in-hospital after clinical assessment:  Discharged Alive  Alive still in-hospital  Died

Date of discharge or death  d  d  m  m  y  y  y  y

ACIOS unique patient ID  / / / /

-----  
Patient name: \_\_\_\_\_

DOB  d  d  m  m  y  y  y  y

Patient hospital number \_\_\_\_\_

Ward \_\_\_\_\_ Bed \_\_\_\_\_

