**Main category for admission:** The main diagnosis or reason that the patient is being treated in hospital.

**Treatment limitations:** A patient has a treatment limitation if the clinical team have made the clinical judgement that some treatments would not be in the patient's best interest. For example "DNR" (do not resuscitate in the event of a cardiac arrest), or "Not for ICU" in the event of deterioration.

**Days in hospital:** Total number of days in hospital from admission.

**Status at hospital discharge or 7th day in-hospital after clinical assessment:** The survival status of the patient at hospital discharge, or at the 7th day after clinical assessment (if the patient had not yet been discharged). The study is censored at the 7th day after clinical assessment.

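### Length of hospital stay is a secondary outcome cut off at day 7, but the only summary rule supplied for it handles neither open stays nor stays that end in death

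*Protocol*

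**What the plan says.** Protocol section 5.5 lists "Length of hospital stay" as a secondary outcome, with no start point, end point or target quantity. The Summary (section 3) stops follow-up 7 days after inclusion, and section 7.3.4 names three end states: discharged alive, died, or alive and still in hospital.

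Three places bear on how a stay is timed:

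- Section 8, on 1-day and 7-day outcomes, runs from inclusion "to hospital discharge or death, censored at 7-days".
- The follow-up part of the patient CRF (Appendix 2b) asks for "Total days in hospital from admission to discharge" and has one end-date field, "Date of discharge or death".
- The CRF definitions give days in hospital as "Total number of days in hospital from admission", with no end. The next definition says that the study is censored at the seventh day after clinical assessment.

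For analysis, section 10.2 says "Continuous variables will be described as mean and standard deviation if normally distributed, or median and inter-quartile range if not normally distributed" and adds "Comparisons of continuous variables between groups will be performed using t-tests, one-way ANOVA or equivalent non-parametric tests as appropriate". It also promises more detail: "An ACIOS statistical analysis plan (SAP) will be written prior to inspection of the final dataset". The SAP supplied covers only the pain sub-study. Its section 3.1 repeats the summary rule, and its one time-to-event analysis concerns mortality.

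**The concern.** The census takes in everyone who is in a bed on one day and follows them for a week. At the end, some stays are still open and others have ended in death. A mean or median needs one number per patient, and for these two groups the number depends on a choice that the supplied documents do not make. Open stays could be cut at day 7 or left out. Deaths could count as completed stays or be dropped.

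Two things are at stake. If the reader takes the result as total stay, both ways of treating open stays tend to give too low a figure when many are open. If groups with different mortality are compared, deaths shorten the apparent stay, so a shorter mean or median cannot be read as faster recovery. The groups that this study naturally forms, by critical illness and by receipt of essential care, are the ones whose mortality it sets out to study.

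**Working it through.** The documents state no figure for length of stay, so there is nothing to reproduce. Every input below is an assumption except the 7-day limit.

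**Step 1. Which text settles the timing?**

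| Place | Start | End | Names length of stay? |
|---|---|---|---|
| Section 8 | inclusion | discharge or death, censored at day 7 | no |
| CRF field for days | admission | discharge | records it; silent on deaths and open stays |
| CRF end-date field | – | discharge or death | no |
| CRF definition of days | admission | not given | silent on deaths and open stays |

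Read together, these suggest that death ends a stay and that open stays are censored at day 7. They do not agree on the start, and none says how a censored value enters a mean or median.

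**Step 2. Open stays, no deaths.** Let stays be exponential with mean *m*. For a patient present on the census day, elapsed and remaining stay are then independent and each exponential with mean *m*.

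- Share open at day 7: e^(−7/m).
- Median total stay: solve (1 + x/m)·e^(−x/m) = 1/2, so x = 1.678·m.
- Median with open stays cut at day 7, for x above 7: x = m·ln[2(1 + 7/m)].
- Median of completed stays only, for x above 7: x = m·ln[2(7/m)/(1 − e^(−7/m))].

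For m = 7 the cut median is 7·ln 4 = 9.7, and the completed-only median is 7·ln(2/0.632) = 8.1. For m = 14 they are 14·ln 3 = 15.4 and 14·ln(1/0.393) = 13.06. For m = 3 the median of 5.0 lies below 7, so cutting cannot move it. The completed-only median then solves 1 − (1 + x/3)·e^(−x/3) = 0.5·(1 − e^(−7/3)), which gives 4.6.

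| Assumed mean stay (days) | Open at day 7 | Median total | Cut at day 7 | Completed only |
|---|---|---|---|---|
| 3 | 10% | 5.0 | 5.0 (0% low) | 4.6 (9% low) |
| 7 | 37% | 11.7 | 9.7 (17% low) | 8.1 (31% low) |
| 14 | 61% | 23.5 | 15.4 (35% low) | 13.06 (44% low) |

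With lognormal stays (same means, sigma 0.8), simulation gives 0% / 11% / 29% low when cut and 8% / 27% / 41% low for completed stays only.

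**Step 3. Deaths, if groups were compared.** Let live discharge have rate λ per day and death rate d, with h = λ + d. Elapsed stay is exponential with mean 7 days in both groups. Choose d so that (d/h)·(1 − e^(−7h)) equals the assumed 7-day mortality. Live discharge by day 7 is then (λ/h)·(1 − e^(−7h)). The reference group has 3% mortality and λ = 1/7, so d = 0.0069, live discharge is 62% and the median stay from admission, cut at day 7, is 9.6 days. The comparison group has 20% mortality:

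| λ in comparison group | d | Median cut at day 7 | Live discharge by day 7 |
|---|---|---|---|
| 1/7 | 0.0524 | 9.1 v 9.6 | 55% v 62% |
| 1/10 | 0.0456 | 9.7 v 9.6 | 44% v 62% |
| 1/14 | 0.0413 | 10.1 v 9.6 | 35% v 62% |

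In the first row the recovery rates are equal, yet the group with more deaths looks faster. In the second, near-equal medians sit beside a gap in live discharge of 62 − 44 = 18 points. With a smaller mortality gap (10% v 3%, equal λ), the medians are 9.4 v 9.6, so the effect is slight.

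**The case against.** The strongest reply is that the protocol defers detail to a main-study SAP that is not among the documents and may already hold a rule. That stands. A reader might infer that the study has no rule for length of stay, but the documents support only the statement that the supplied ones contain none.

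Second, the end of a stay is not wholly undefined. Section 8, the CRF end-date field and the CRF statement on censoring point to death as an end and day 7 as the censoring time. That also stands, and it narrows the gap to the start point and to how censored and fatal stays are summarised.

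Third, understatement presumes that total stay is the target. For observed stay up to day 7, the cut value is not biased. The protocol never states the target, so the percentages above are conditional on it.

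Fourth, a reader might infer that a biased comparison of stay is planned. Section 10.2 permits group tests of continuous variables without exempting length of stay, but the outcome appears in no objective or research question (sections 5.2 and 5.3). The death scenarios therefore show what could happen. Moreover, the three status proportions in section 7.3.4, if shown by group, would reveal the gap in live discharge.

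What remains is that a mean or median with t-tests, ANOVA or rank tests does not suit a time that is cut off at day 7 and may end in death.

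**Conclusion.** The point holds as a minor one. The supplied documents apply a general continuous-variable rule to a secondary outcome that is censored at day 7 and can end in death, and they leave its clock unreconciled between inclusion and admission. If total stay is meant, the effect on the cut median runs from nil at an assumed mean of 3 days to about 35% low at 14 days. For completed stays only, it runs from 9% to 44% low. These sizes rest wholly on assumed distributions, and the documents cannot show where in the range the study would fall. The distortion by deaths matters only if groups are compared, and it is small when mortality differs little.

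The documents do not support a claim that the study's main results are at risk: presence of critical illness and 7-day in-hospital mortality are unaffected.

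**What to change.** If the main-study SAP already has a rule, confirm that it covers the points below. If not, add a few sentences to it or to protocol section 10.2:

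- Take length of stay out of the general continuous-variable rule and state its start point.
- Report the cumulative incidence of live discharge from inclusion to day 7, with in-hospital death as a competing event, beside the three day-7 status proportions already planned.
- If days from admission are also shown, give them by day-7 status with the number still in hospital, labelled as stays of patients present on the census day.
- Base any group comparison on discharge alive by day 7.

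No new data are needed: the CRF already records the dates of admission, assessment and discharge or death, and status at day 7. The cost is that the main result is no longer a single average total stay. This is a cheap improvement.
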